7.1.3. Population of Interest

ORR at primary analysis will be analyzed using both ITT and Efficacy population for frozen liquid cohort, and Lyo population for lyophilized cohort.

7.1.4. Statistical Analyses / Methods

Details of the planned displays are provided in [Appendix 13](#): List of Data Displays and will be based on GSK data standards and statistical principles.

7.2. Secondary Efficacy Analyses

7.2.1. Endpoint / Variables

7.2.1.1. ORR based on Investigator Assessment

ORR based on investigator-assessed response will be analysed as one of the secondary endpoints.

ORR at primary analysis will be analyzed based on the confirmed responses, which will be derived based on the algorithm specified in [Table 3](#).

ORR at IA should also be analyzed based on confirmed responses if available. However, in case a participant has achieved a response of PR or better at data cut, which was not confirmed due to the time constraints (too short timeframe for the next assessment) but with a potential to be confirmed through subsequent assessments after interim, the participant will also be considered as a responder; if the participant dies or discontinues study or starts other anti-cancer therapy prior to confirming the response, the participant will not be considered as a responder at IA.

7.2.1.2. Clinical Benefit Rate (CBR)

CBR is defined as the percentage of participants with a confirmed minimal response (MR) or better, according to the IMWG Response Criteria [[Kumar, 2016](#)]. CBR will be summarized in the same way as ORR. No hypothesis testing will be performed for CBR. At primary analysis, CBR based on both IRC and investigator assessment will be summarized. At interim analysis, only CBR based on investigator assessment will be summarized.

7.2.1.3. Duration of Response (DoR)

DoR is defined as the time from first documented evidence of confirmed PR or better until the earliest date of confirmed disease progression (PD) per IMWG, or death due to PD among participants who achieve a response (i.e., confirmed PR or better). Responders without confirmed PD will be censored at the censoring time point for Time to Progression as specified in [Table 5](#) of Section [7.2.1.6](#).

DoR will be analysed at the time of final ORR analysis, also at study close out if applicable, based on responses assessed by both IRC and investigator.

7.2.1.4. Time to Response (TTR)

TTR is defined as the time between the date of randomization and the first documented evidence of confirmed response (PR or better), among participants who achieve a response (i.e., confirmed PR or better).

TTR will be analysed at the time of final ORR analysis, based on responses assessed by both IRC and investigator.

7.2.1.5. Progression Free Survival (PFS)

PFS is defined as the time from randomization until the earliest date of confirmed PD per IMWG, or death due to any cause.

PFS will be analysed at the time of final ORR analysis, also at study close out if applicable, based on responses assessed by both IRC and investigator.

A summary of the assignments for progression and censoring dates for PFS are specified in [Table 4](#) below.

Table 4 Assignments for Progression and Censoring Dates for PFS Analysis

Situation	Date of Event (Progression/Death) or Censoring	Outcome Event (Progression/Death) Or Censored
No (or inadequate) baseline tumor assessments ^[1] and the subject has not died (if the subject has died follow the rules for death indicated at the bottom of the table)	Randomization	Censored
No post-baseline assessments and the subject has not died (if the subject has died follow the rules for death indicated at the bottom of the table)	Randomization	Censored
Progression documented without extended loss-to-follow-up time	Date of assessment of progression ^[1]	Event
No progression (or death)	Date of last 'adequate' assessment of response ^[2]	Censored
New anticancer treatment started (prior to documented disease progression or death) ^[3] .	Date of last 'adequate' assessment of response ^[2] (on or prior to starting anti-cancer therapy)	Censored
Death without extended loss-to-follow-up time	Date of death	Event
Death or progression after an extended loss-to-follow-up time (two or more missed cycles + 7 day window) ^[4]	Date of last 'adequate' assessment of response ^[2] prior to PD/death (prior to missed assessments)	Censored

Situation	Date of Event (Progression/Death) or Censoring	Outcome Event (Progression/Death) Or Censored
Death or progression after an extended loss-to-follow-up time from randomization	Date of randomization	Censored

[1] Adequate baseline assessment is defined as at baseline, a patient has at least one of the following measurements:
a. Serum M-protein ≥ 0.5 g/dL (≥ 5 g/L) or b. Urine M-protein ≥ 200 mg/24h or c. Serum FLC assay: Involved FLC level ≥ 10 mg/dL (≥ 100 mg/L) and an abnormal serum free light chain ratio (<0.26 or >1.65)

[2] An adequate assessment is defined as an assessment where the IRC/Investigator determined response is sCR, CR, VGPR, PR, MR, or SD.

[3] If PD or death and New anti-cancer therapy occur on the same day assume the progression or death was documented first (e.g., outcome is progression or death and the date is the date of the assessment of progression or death). If anti-cancer therapy is started prior to any adequate assessments, censoring date should be the date of randomization.

[4] Refer to Section 15.5.4 “Extended Loss to Follow-up or Extended Time without an Adequate Assessment”.

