1. Subsequent disease assessment is defined as the next adequate (not missing or NE) disease assessment following the first timepoint before (or on the same date of) start of new anti-cancer therapy except for confirmation of PD, for which PD or death due to PD after new anti-cancer therapy are considered for confirmation of PD. No minimal time interval is required for the subsequent disease assessment, but a different sample is required for confirmation.
2. SD does not need to be confirmed.
3. PD due to imaging (i.e., plasmacytoma or bone lesion) does not need to be confirmed.
4. Where criteria are not mutually exclusive, take the first that applies.

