7.2.1.6. Time to Progression (TTP)

TTP is defined as the time from randomization until the earliest date of confirmed PD per IMWG, or death due to PD.

TTP will be analysed at the time of final ORR analysis, also at study close out if applicable, based on responses assessed by both IRC and investigator.

A summary of the assignments for progression and censoring dates for TTP are specified in Table 5.

Table 5 Assignments for Progression and Censoring Dates for TTP Analysis

Situation	Date of Event (Progression/Death) or Censoring	Outcome Event (progression/Death) Or Censored
No (or inadequate) baseline tumor assessments ^[1] and the subject has not died (if the subject has died follow the rules for death indicated at the bottom of the table)	Randomization	Censored
No post-baseline assessments and the subject has not died (if the subject has died follow the rules for death indicated at the bottom of the table)	Randomization	Censored

Situation	Date of Event (Progression/Death) or Censoring	Outcome Event (progression/Death) Or Censored
Progression documented at or between scheduled visits	Date of assessment of progression ^[1]	Event
No progression (or death)	Date of last 'adequate' assessment of response ^[2]	Censored
New anticancer treatment started (prior to documented disease progression or death) ^[3] .	Date of last 'adequate' assessment of response ^[2] (on or prior to starting anti-cancer therapy)	Censored
Death due to progression without extended loss-to-follow-up time	Date of death	Event
Death from causes other than progression without extended loss-to-follow-up time	Date of death	Censored
Death or progression after an extended loss-to-follow-up time (two or more missed cycles + 7 day window) ^[4]	Date of last 'adequate' assessment of response ^[2] prior to PD/death (prior to missed assessments)	Censored
Death or progression after an extended loss-to-follow-up time from randomization	Date of randomization	Censored

Adequate baseline assessment is defined as at baseline, a patient has at least one of the following measurements: a. Serum M-protein ≥ 0.5 g/dL (≥ 5 g/L) or b. Urine M-protein ≥ 200 mg/24h or c. Serum FLC assay: Involved FLC level ≥ 5 mg/dL (≥ 50 mg/L) and an abnormal serum free light chain ratio (<0.26 or >1.65).

An adequate assessment is defined as an assessment where the IRC/Investigator determined response is sCR, CR, VGPR, PR, MR, or SD.

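### Tables 4 and 5 do not say whether an inadequate baseline or a documented imaging progression prevails, and duration of response can inherit a censoring date before the response (minor)

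*SAP*

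**What the plan says.** **PFS and TTP (SAP 7.2.1.5, Table 4; 7.2.1.6, Table 5).** Row 1 of each table covers a missing or inadequate baseline "and the subject has not died (if the subject has died follow the rules for death indicated at the bottom of the table"). The assigned date is randomization and the outcome is censored.

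Each table also has a progression row with outcome event, dated at the progression assessment. Table 4 words it "Progression documented without extended loss-to-follow-up time" and Table 5 "Progression documented at or between scheduled visits". Neither wording requires an adequate baseline.

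**Adequate baseline.** The Table 4 footnote reads "Adequate baseline assessment is defined as at baseline, a patient has at least one of the following measurements" and then lists serum M-protein, urine M-protein, and involved FLC with an abnormal ratio. Imaging is not listed. The FLC limit is "Involved FLC level ≥ 10 mg/dL (≥ 100 mg/L") in Table 4 and "Involved FLC level ≥ 5 mg/dL (≥ 50 mg/L") in Table 5.

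**Imaging progression (7.1.1.1, Table 3).** Row 16 classes it as PD whatever follows, and the notes say "PD due to imaging (i.e., plasmacytoma or bone lesion) does not need to be confirmed".

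**DoR (7.2.1.3).** Confirmed PD or death due to PD is the event. Otherwise, "Responders without confirmed PD will be censored at the censoring time point for Time to Progression as specified in" Table 5.

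**The concern.** Row 1 makes sense where progression can only be judged against a measurable baseline marker. A new plasmacytoma or bone lesion can be judged without one, and Table 3 treats it as PD outright. If row 1 is applied to such a participant, the PD stands in the best-response table while PFS and TTP are censored at day 0. If the progression row is applied, the same data give an event. Two programmers could follow the SAP and disagree.

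The DoR problem is separate and concerns other participants. DoR starts at the first response, but the Table 5 date that it borrows can be the randomization date. Nothing in 7.2.1.3 stops the censoring date from preceding the start of the interval.

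**Working it through.** The plan gives no figure to reproduce here. The check applies the stated rules to constructed participants. Randomization is day 0 and all participant dates are assumptions for illustration.

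**Inputs.** Table 4 and Table 5 rows; the 49-day extended-loss window (15.5.4: 6 × 7 + 7 = 49); the DoR rule in 7.2.1.3; Table 3, row 16 and its notes.

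**A. Alive, inadequate baseline, imaging PD on day 84, last adequate assessment on day 63.**
- The gap is 84 - 63 = 21 days, within 49, so the extended-loss row does not apply.
- Row 1: censored, day 0.
- Progression row: event, day 84.
- Both rows match. The instruction to take the first criterion that applies is a note to Table 3; Tables 4 and 5 have none.
- The date cell of Table 4's progression row carries marker [1], which is the adequate-baseline footnote. That may be a misplaced marker, but it could also be read as a condition on the row.

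**B. Alive, inadequate baseline by Table 5, confirmed response from day 42, no PD, no new therapy, last adequate assessment on day 210.**
- Row 1: DoR = 0 - 42 = -42 days (-41 if the first day is counted).
- No-progression row: DoR = 210 - 42 = 168 days (169 if the first day is counted).
- In general row 1 gives minus the day of first response: -21 for a response on day 21, -126 for day 126.

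**C. As B, but with imaging PD on day 210 and last adequate assessment on day 189.**
- DoR is an event by definition at 210 - 42 = 168 days (169 if the first day is counted). It does not use the Table 5 censoring date.
- Row 1 would still censor TTP at day 0, so the two endpoints would disagree for one person.

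**D. As A, but died on day 100.** Row 1 drops out because of the death exception, and an event is recorded.

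**Can anyone be in row 1 and also be a responder?** The SAP does not exclude it. ITT has no baseline condition (Section 4), and the confirmation algorithm in Table 3 has none. Baseline is the latest non-missing pre-dose value (5.2), so a participant could be above a threshold earlier in screening and below it at baseline.

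**Do the two tables select the same people?** No. Involved FLC of 50 to below 100 mg/L, with an abnormal ratio and no other qualifying measurement, is inadequate for PFS but adequate for TTP and hence DoR.

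**Size for PFS if row 1 is applied.** Let S be the true 6-month PFS. Let f be the joint share of an arm with a sub-threshold baseline, alive at the cut-off, and with imaging PD within 6 months. With no other early censoring, the overstatement is S/(1 - f) - S. The SAP gives neither value, so these are assumptions:

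| f | S | Overstatement |
|---|---|---|
| 0 | any | 0 |
| 0.01 | 0.25 | 0.25/0.99 - 0.25 = 0.0025 |
| 0.03 | 0.35 | 0.35/0.97 - 0.35 = 0.011 |
| 0.05 | 0.45 | 0.45/0.95 - 0.45 = 0.024 |

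**The case against.** **The SAP does not order the progression to be removed.** A reader might infer that every such imaging PD disappears from PFS and TTP. The text does not support that: the progression row fits equally well. This stands. What remains is an unresolved conflict between two rows with opposite outcomes.

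**Not every responder with an inadequate baseline gets a negative DoR.** A reader might infer that too, or that the same person loses a PD and gets a negative DoR. Neither follows. Only living responders without confirmed PD can be dated by row 1. A responder with imaging PD or death due to PD is a DoR event, and row 1 excludes anyone who has died. This also stands.

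**The affected group may be empty.** Entry criteria and the detail of response assessment lie in the protocol and response criteria, which are not at hand. They may keep out participants below the thresholds or prevent them from being graded as responders. This stands as a limit on size. It does not make the rule right.

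**Best response and PFS may differ by design.** The 49-day rule already censors some progressions that count as PD in best response. A mismatch is therefore not a defect in itself. But that rule states when it applies, whereas here two rows apply at once.

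**The endpoints are secondary and the primary analysis is past.** The hypothesis tests concern ORR only (2.4), and Sections 9 and 12.2 describe work done at the primary analysis in the past tense. This lowers the priority and adds a cost to any change.

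**Conclusion.** The point holds as a minor defect in two parts.

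1. For a living participant with an inadequate baseline and a documented imaging PD, Tables 4 and 5 permit either censoring at day 0 or an event at the PD date, with no stated precedence.
2. For a living confirmed responder without PD whose baseline fails the Table 5 definition, applying row 1 through the cross-reference in 7.2.1.3 gives a DoR below zero, which is impossible.

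The differing FLC limits mean that row 1 also selects different participants for PFS and for TTP.

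The number affected is not stated. As an assumption, 0 to 5% of about 100 per arm would be 0 to 5 participants per arm. Over the illustrated range, the effect on 6-month PFS runs from nothing to about 2.4 percentage points, and only if row 1 is the row applied. ORR does not use these tables. PFS, TTP and DoR are summarised by Kaplan-Meier methods without a planned test.

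**What to change.** - **Tables 4 and 5, row 1:** add that the row does not apply when PD due to imaging is documented. Such participants then follow the existing progression, new-therapy and extended-loss rows unchanged.
- **Section 7.2.1.3:** state that row 1 does not apply to confirmed responders, that all other Table 5 censoring rows still apply (including new therapy and death from causes other than progression), and that a DoR censoring date cannot precede the first response.
- **Adequate-baseline footnotes:** reconcile the FLC limit (100 mg/L in Table 4, 50 mg/L in Table 5) so that row 1 selects the same participants in both tables.

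A general top-down order should not be imposed. The progression and no-progression rows precede the new-therapy row, so that row would lose its effect. Table 5's progression row has no extended-loss qualifier, so its later extended-loss row would never apply to a progression.

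The cost is a few sentences and a small programming change. A few participants may be handled differently from the primary-analysis run; if so, the report should list them and give the reason.

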15.5.4. Extended Loss to Follow-up or Extended Time without an Adequate Assessment

For subjects, if two or more scheduled disease assessments are missed and are then followed by an assessment of PD or death, PFS will be censored at the last adequate assessment prior to PD or death. When the scheduled disease assessment is every 3 weeks, a window of 49 days (6 weeks + 7 day window) will be used to determine whether there was an extended time without adequate assessment. That is, if the time difference between PD/death and last adequate assessment is more than 49 days, then PFS will be censored at the last adequate assessment prior to PD/death.

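### The 49-day extended-loss test for PFS ignores an attended visit read as PD, so a later death not due to PD can be censored with fewer than two missed visits

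*SAP*

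**What the plan says.** Four rules in the SAP act together.

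- **Event (Section 7.2.1.5).** PFS runs to "the earliest date of confirmed PD per IMWG, or death due to any cause".
- **Confirmation (Section 7.1.1.1, Table 3).** Row 13 sets a non-imaging PD to NE when the participant dies of a cause other than PD before another adequate assessment. Row 12 treats the PD as confirmed when the death is due to PD. Imaging PD needs no confirmation. For choosing the confirming visit, note 1 says: "Subsequent disease assessment is defined as the next adequate (not missing or NE) disease assessment following the first timepoint".
- **Adequate assessment for PFS (Table 4, footnote 2).** "An adequate assessment is defined as an assessment where the IRC/Investigator determined response is sCR, CR, VGPR, PR, MR, or SD". PD is not listed.
- **Extended loss (Section 15.5.4).** The trigger is first stated as "if two or more scheduled disease assessments are missed and are then followed by an assessment of PD or death". It is then made operational: "When the scheduled disease assessment is every 3 weeks, a window of 49 days (6 weeks + 7 day window) will be used", and "if the time difference between PD/death and last adequate assessment is more than 49 days, then PFS will be censored" at the last adequate assessment.

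The matching row of Table 4 also states the trigger as missed cycles and dates the censoring before the missed assessments. Its last row censors at randomization when the extended loss runs from randomization.

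**The concern.** Section 15.5.4 offers the 49-day gap as a restatement of two missed assessments. The two tests agree only if every attended, evaluable visit restarts the clock. A visit read as PD does not, because footnote 2 leaves PD out. The participant came to the visit and was evaluated, yet the rule counts as if the visit had not taken place.

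This matters when the PD is later set to NE under Table 3 row 13. Death is then the only PFS event left, and it is tested against the visit before the PD. A participant who was seen, read as progressing and then died can be handled as lost to follow-up. PFS counts death from any cause, so a true event is lost, and the censoring is related to the participant's course.

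**Working it through.** **The plan's own figure.** Two 3-week intervals plus a 7-day window: 2 × 21 + 7 = 49 days. This reproduces Section 15.5.4.

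**Worked example, days from randomization.** SD on day 21, non-imaging PD on day 42, day-63 visit missed, death not due to PD on day 75.

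1. Table 3 row 13: the PD becomes NE, so only the death can be an event.
2. Last adequate assessment under footnote 2: day 21.
3. Gap: 75 − 21 = 54 > 49, so PFS is censored at day 21.
4. Scheduled visits missed: one (day 63). The missed-visit trigger is not met, and by that test the death is an event at day 75.
5. Counted from the PD visit: 75 − 42 = 33 ≤ 49, so the event is kept.

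**No earlier SD-or-better visit.** First assessment PD on day 21, non-PD death on day 60 with no further adequate assessment. From randomization the gap is 60 > 49, so the last row of Table 4 censors at randomization. From the PD visit the gap is 60 − 21 = 39, so the death would be an event.

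**Range of the effect.** Here day 0 is the last SD-or-better visit, with visits due on days 21, 42, 63 and 84. All deaths are from causes other than PD, and an attended NE visit is not counted as missed.

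| Pattern | Deaths censored with fewer than two missed visits | Missed visits | Days from PD to death | Deaths that become events if the PD visit restarts the clock |
|---|---|---|---|---|
| A: PD day 21, day 42 missed | days 50–63 | 1 | 29–42 | days 50–70 |
| B: day 21 missed, PD day 42 | days 50–63 | 1 | 8–21 | days 50–91 |
| C: PD day 21, NE day 42 | days 50–84 | 0–1 | 29–63 | days 50–70 |
| D: NE day 21, PD day 42 | days 50–84 | 0–1 | 8–42 | days 50–91 |

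The upper limits in the last column are 21 + 49 = 70 and 42 + 49 = 91. If SD came exactly 21 days before the PD, a death up to 28 days after the PD stays an event, since 21 + 28 = 49 does not exceed the window.

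**Direction.** Take n at risk at the censoring date, m other events before the death, and no other censoring. Just before the death date, survival is (n − m)/n if the death is kept as an event and (n − 1 − m)/(n − 1) if the participant is censored early. With n = 100 and m = 50 for illustration, these are 0.500 and 49/99 = 0.495. From the death date onward they are 49/100 = 0.490 and 49/99 = 0.495. Early censoring lowers the curve slightly before the death and raises it afterwards.

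**The case against.** The strongest reply is that the rule reaches very few participants and none of the formal inference. Most of this stands.

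- **Deaths due to PD.** A reader might infer that deaths from myeloma soon after progression are dropped. They are not. Row 12 confirms the PD when death is due to PD, and imaging PD needs no confirmation. Both remain events at the PD date, subject to the ordinary gap before that PD.
- **PD at the first assessment.** A reader might infer that this always leads to censoring at randomization. It does so only if the PD is non-imaging and unconfirmed, and a non-PD death falls more than 49 days after randomization.
- **Direction.** A reader might infer a bias that always flatters PFS. The calculation above does not support that: a median or 6-month rate falling between the censoring date and the death date moves slightly the other way.
- **Two meanings of adequate.** Table 3 note 1 and Table 4 footnote 2 define the word for different purposes, and leaving PD out is sensible when choosing a censoring date. The difference is not in itself a contradiction. The conflict lies within Section 15.5.4, and between its 49-day test and the Table 4 row.
- **Importance.** The hypothesis tests concern ORR within each arm (Section 2.4), and ORR is untouched. PFS is summarized by Kaplan-Meier. Table 2.0140 gives reasons for censoring, and Listings 1.0430 and 1.0440 show PFS by participant, so affected cases could be found.

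None of this removes the mismatch: followed as written, the 49-day sentence censors a death that the missed-visit sentence keeps.

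**Conclusion.** The point holds within narrow limits. It needs a non-imaging PD, no further adequate assessment, a death not due to PD, and more than 49 days from the last SD-or-better visit (or from randomization if there is none) to the death. Under those conditions PFS is censored at the earlier date with as few as zero missed visits. The zero-visit case assumes that an attended NE visit is not counted as missed. The lower limit is 8 days after the PD if the visit before it was missed or NE, and 29 days if visits up to the PD were on a 3-week schedule.

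The number of participants affected cannot be derived from the SAP. Each one loses a true PFS event, which raises the curve from the death date onward after a slight dip before it. Table 5 repeats the footnote, but non-PD deaths are censored for TTP in any case. Only censoring dates change there (day 75 becomes day 21 in the example), and likewise for DoR in responders, because DoR takes its censoring from Table 5. The rule is worth correcting because it contradicts its own stated trigger, not because a main conclusion depends on it.

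**What to change.** For the extended-loss test only, change Section 15.5.4 in one of two ways:

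1. measure the 49 days from the last attended assessment whose raw IRC or investigator visit response is evaluable, including a PD that is later left unconfirmed; or
2. count missed scheduled assessments directly.

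Option 1 must name the raw visit response. Row 13 relabels exactly these PDs as NE, so a bare reference to assessments that are not missing or NE could still exclude them. The two options are not identical. In pattern C, deaths on days 71–84 stay censored under option 1, because the NE visit does not restart the clock, but are kept under option 2 if an attended NE visit is not a missed one. The SAP should choose one option and say how NE visits count.

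Keep the sCR-to-SD list for setting censoring dates, and use the same wording in Tables 4 and 5. The cost is a wording edit and a small change to the derivation, with no new data.
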